6. DATA CONVENTIONS

The following analysis conventions will be used in the statistical analysis.

6.1. Definition of Baseline for Efficacy/Safety Variables

Unless otherwise specified, the Baseline assessment for all measurements will be the latest available valid measurement taken prior to the administration of investigational product.

6.2. Data Handling Convention for repeat measurements

Orthostatic Hypotension data

This applies specifically to the data handling of repeat measurements in the assessment of orthostatic hypotension. Per protocol, if the initial vital assessments for orthostatic hypotension is consistent with the definition of orthostatic hypotension, the supine, standing blood pressure or pulse should be repeated up to 2 more times. The guidelines for the repeat assessments are shown below:

Initial Assessment	Repeat Assessment 1	Repeat Assessment 2	Does Patient meet OH criteria	Value to be used in the analysis
Does not meet OH definition	N/A	N/A	No	Initial Assessment
Meets OH definition - repeat	Does not meet definition - repeat	Does not meet definition	No	Repeat Assessment 2
Meets OH definition - repeat	Does not meet definition - repeat	Meets OH definition	Yes, AE of OH reported.	Repeat Assessment 2
Meets OH definition - repeat	Meets OH definition	N/A	Yes, AE of OH reported.	Repeat Assessment 1

Baseline for the assessment of orthostatic hypotension vital assessments uses the last available assessment prior to the start of study drug. Measurements post baseline will not be averaged. Rather frequency counts for patients meeting criteria for orthostatic hypotension will reflect the scenario as shown in the table.

Patient reported outcomes data

Should there be duplicate data entries for PRO diary data, the first entry for the day will be used.

6.3. Data Handling Convention for Missing Data

Missing/Incomplete AE/Concomitant medication dates

Imputation of AE and Concomitant Missing and Partial start dates:

Every effort will be made to collect the start dates of all AEs and concomitant medications. However, in the case the start date of an AE or concomitant medication is incomplete or missing,

it will be assumed to have occurred on or after the first dose of study medication, except if an incomplete date (e.g., month and year) clearly indicates that the event started prior to treatment. If the partial date indicates the same month or year of the first dose of study medication date, then the start date of the first dose will be imputed, otherwise, the missing day or month by the first day or the first month will be imputed.

Imputation of Partial AE and concomitant Medication Partial end dates:

When only year is present, missing AE/concomitant medication end day and month will be imputed to the earlier of (study end date, 31DECYYYY).

When both month and year present, missing AE/concomitant medication end day will imputed to the last day of the month.

There will be no attempt to impute completely missing AE or concomitant medication end dates. Events with an end date missing will be assumed to be ongoing at the time of data cut off.

Missing/Incomplete Medical history dates

Medical history start dates are used to determine the duration of chronic back pain at baseline per eCRF data. Completing missing medical history dates will not imputed. Missing month will be imputed to January and missing day will be imputed to the first day of the month.

Adverse event

If the intensity of a TEAE is missing, it will be classified as “severe” in the frequency tables by intensity of TEAEs. If the assessment of relationship of a TEAE to the investigational product is missing, it will be classified as related to the investigational product.

Other safety data

For laboratory results below the quantification (LOQ), half of the LOQ will be imputed for calculating the descriptive summary.

No imputations for missing laboratory data, ECG data, vital sign data, or physical examination data will be made.

Date of first / last injection

Date of first injection is the first non-missing start date of dosing recorded in the CRF “Investigational Product” module.

If a patient’s date of the last dose is totally missing or unknown, his/her last visit date in the treatment period will be substituted.

Missing item data for questionnaires

LBPI NRS

Baseline average daily LBPI NRS score is defined as the average of the non-missing daily LBPI NRS scores for 5 days prior to randomization (from Day -4 to Day 1). For each week, the average daily LBPI score is defined as the average of the non-missing daily LBPI NRS scores for the 7days before and including the visit day .

RMDQ

CONFIDENTIAL

RMDQ total score will be set to missing if any item is missing.

SF-36

The Half-Scale rule will be used to impute missing item responses in the SF-36 subscale scores i.e. a score will be computed if the respondent answers at least 50% of items in that scale. The missing items in the scale will be imputed by the mean of available items rounded to the nearest whole number.

The bodily pain subscale consists of Q7 and Q8 of the instrument. Since Q7 is based on 6pt Likert score and Q8 is based on a 5pt Likert scale and because mean imputation will be meaningless, the bodily pain subscale score will not be imputed if any of the questions making up the scale is missing.

EQ-5D-5L

Index will be set to missing if any of the 5 dimensions is missing.

MOS-Sleep

MOS-Sleep subscale scores will be computed if at least 50% of items are available. The missing items will be imputed by the mean of available items.

6.4. Data handling for the SF-36 instrument.

Due to scoring differences amongst the instrument's 36 items, 10 of the items will need to be reverse coded to ensure consistency in reporting such that higher scores are indicative of better health. The SF-36 items needing reverse coding are: Q1, Q6, Q7, Q8, Q9a, Q9d, Q9e, Q9h, Q11b, Q11d.

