4.2.1. Inclusion Criteria

A patient must meet the following criteria to be eligible for inclusion in the study:

1. Male or female ≥ 35 years of age at the screening visit
2. Provide signed informed consent
3. Body mass index ≤ 39
4. Clinical diagnosis of chronic moderate to severe LBP (non-radiculopathic) for ≥ 3 months (prior to the screening visit)
 - Quebec taskforce category 1 (pain without radiation) or category 2 (pain with proximal radiation above the knee)
 - Primary pain location between 12th thoracic vertebra and lower gluteal fold
 - At both the screening and the randomization visit, an LBPI NRS score of ≥ 4 over the previous 24 hours
 - During the pre-randomization period, mean daily LBPI score of ≥ 4

- At the screening visit, PGA of LBP of fair, poor or very poor
5. History of regular analgesic medication, such as NSAIDs, COX-2 inhibitors, opioids, paracetamol/acetaminophen, or a combination thereof
 - Taking medication >4 days per week in the month prior to screening
 - Willing to discontinue current opioid pain medications starting at pre-randomization visit through the week 16 study visit
 - Willing to discontinue current NSAID pain medications (oral or topical) starting at pre-randomization visit through 16 weeks after last dose of study drug
 6. A history of inadequate pain relief or intolerance to analgesics used for chronic LBP as defined by:
 - Intolerance or inadequate pain relief from paracetamol/acetaminophen, and
 - Intolerance or inadequate pain relief from at least 1 oral NSAID, and
 - Intolerance or inadequate pain relief from at least 1 opioid, unwillingness to take opioid therapy or lack of access to opioid therapy
 7. Willing to consider TJR surgery, if necessary
 8. Willing and able to comply with clinic visits and study-related procedures
 9. Able to understand and complete study-related questionnaires

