4.3. Pre-Treatment / Concomitant Medication

Medications and procedures will be recorded from the day of informed consent until the EOS visit. Medications will be coded to the ATC level 2 (therapeutic main group) and ATC level 4 (chemical/therapeutic subgroup), according to the WHO Drug Dictionary (WHODD) March 2015 version. Prior medications are defined as medications starting prior to the first

administration of study drug. Prior procedures are defined as procedures performed prior to the first administration of study drug.

Concomitant medications are defined as medications starting prior to *or* during the on-treatment period (as defined in [section 4.5](#)) and ending during or after the on-treatment period.

Post treatment medications are medications starting after the on-treatment period.

Prohibited medications include medications containing NSAIDS (oral or topical; except up to 100mg/day of aspirin for cardiac prophylaxis) and opioid analgesic medications (including tramadol). Opioid analgesic medications (including tramadol) are prohibited through the week 16 study visit. Patients will be directed not to take concomitant medications that contain NSAIDS (oral or topical, except up to 100mg/day of aspirin, which is permitted for cardiac prophylaxis) until at least 16 weeks after the last dose of study drug. Other excluded drugs include:

- Any other investigational agent
- Cyclosporine
- Azathioprine
- Medical marijuana
- Tumor necrosis factor antagonists
- Corticosteroids (topical and inhaled formulations are permitted)
- Tocilizumab
- Abatacept
- Cyclobenzaprine, carisoprodol, orphenadrine, tizanidine
- Muscle relaxants

Prohibited concomitant medications will be summarized separately by ATC class, preferred term and treatment group.

Patients will be counted once in all ATC categories linked to the medication.

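### SAP 6.3 imputes incomplete start dates to on or after first dose without checking the stop date, so an adverse event that ended before dosing counts as treatment-emergent and a drug stopped before dosing can fall outside every medication table

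*SAP*

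**What the plan says.** **Start dates.** For an AE or concomitant medication with an incomplete or missing start, SAP 6.3 sets the default that "it will be assumed to have occurred on or after the first dose of study medication". The one exception is "except if an incomplete date (e.g., month and year) clearly indicates that the event started prior to treatment". Where the partial date shares the month or year of first dose, "then the start date of the first dose will be imputed"; otherwise the missing day or month becomes the first. Protocol 9.6 has the same rule.

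**End dates.** SAP 6.3 handles these in a separate paragraph: "When both month and year present, missing AE/concomitant medication end day will imputed to the last day of the month". A year-only end becomes the earlier of study end and 31 December. Nothing links the imputed start to the end.

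**How the dates are used.** SAP 5.8.1 counts an AE as treatment-emergent if it developed or worsened in the on-treatment period, which SAP 5.8 starts on the day of first dose. There is no condition on the end date. In SAP 4.3, "Prior medications are defined as medications starting prior to the first" dose. Concomitant medications start before or during the on-treatment period, with the added condition "and ending during or after the on-treatment period". Post-treatment medications start after that period. SAP 5.3 tabulates prior, concomitant, post-treatment and on-study medications, the last being concomitant plus post-treatment. SAP 4.3 adds a summary of prohibited concomitant medications.

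**The concern.** The first-dose default is a sensible precaution when an event's timing is unknown. It is not one when a recorded end date shows that the event was over before dosing. AEs are collected from consent (SAP 4.5.1), so such records can arise, and the percentage of patients with TEAEs is a named safety endpoint (Protocol 8.2).

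For medications the design itself creates the pattern. Inclusion criterion 5 requires regular analgesic use ("Taking medication >4 days per week in the month prior to screening"), and NSAIDs and opioids are to be stopped at the pre-randomization visit (Protocol 3.1 and 5.7.2). If a stopped drug with an incomplete start is pushed to first dose, the prior-medication table loses part of the analgesic background that describes this population, and no other table picks it up.

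**Working it through.** The plan states no figure on this point, so there is none to reproduce. The check traces records through the written rules.

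**Definitions.** Let F be first dose, T the end of the on-treatment period, S the start and E the end used in analysis.
- TEAE: F ≤ S ≤ T (SAP 5.8 and 5.8.1)
- Prior: S < F (SAP 4.3)
- Concomitant: S ≤ T and E ≥ F (SAP 4.3)
- Post-treatment: S > T (SAP 4.3)
- On-study: concomitant or post-treatment (SAP 5.3)

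**Assumed dates, for illustration.** Case A: F = 20 June 2016, true stop 13 June. Case B: F = 4 June 2016, true stop 28 May. Both stops are 7 days before first dose, which is day -7 because there is no day 0. For a wholly missing start the SAP says on or after first dose without naming a date; F is used here.

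| Case | Start recorded | End recorded | S | E | As an AE | As a medication |
|---|---|---|---|---|---|---|
| A | missing, 2016, or June 2016 | 13 June 2016 | 20 June | 13 June | TEAE | no table |
| A | same | June 2016 | 20 June | 30 June | TEAE | Concomitant |
| A | same | 2016 | 20 June | 31 Dec | TEAE | Concomitant |
| A | March 2016 | 13 June 2016 | 1 March | 13 June | pre-treatment | Prior |
| A | 2014 | 13 June 2016 | 1 Jan 2014 | 13 June | pre-treatment | Prior |
| B | missing or 2016 | 28 May 2016 | 4 June | 28 May | TEAE | no table |
| B | missing or 2016 | May 2016 | 4 June | 31 May | TEAE | no table |
| B | missing or 2016 | 2016 | 4 June | 31 Dec | TEAE | Concomitant |

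**First row in full.** S = 20 June and E = 13 June, so the record ends 7 days before it starts. As an AE, F ≤ S holds, so it is a TEAE. As a medication, S < F fails, so it is not prior. E ≥ F fails, so it is not concomitant. S > T fails, so it is not post-treatment. It is therefore not on-study and not in the prohibited concomitant summary either: 0 of 5 tables.

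**Does the rule reach a drug stopped on day -7?** The rule names concomitant medication. Protocol 5.7 uses that term for any treatment from screening to week 36, so the rule applies and the table above follows. SAP 4.3 uses it only for drugs that end during or after the on-treatment period. On that reading a drug stopped on day -7 is outside the rule, and nothing else in the SAP says how to impute its start.

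**After the correction.** Capping S at E when E is before F moves the three rows marked no table to pre-treatment AE and to the Prior table. The other rows do not change.

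**The case against.** The strongest reply is that the rule is narrower than it looks and touches only descriptive output. Much of this stands.

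- A reader might infer that any start in the dosing year is affected. It is not: a known earlier month is protected by the exception, and a year-only start in an earlier year becomes 1 January of that year. Long-standing analgesics with even the year known are therefore usually safe. The sentence about the same month or year does sit awkwardly beside the exception when the month is known and earlier.
- A reader might infer that a given share of prior-analgesic records is lost. The documents give no rate of incomplete dates, and SAP 6.3 says every effort will be made to collect them. Complete loss also needs an end that resolves to before first dose; with other partial ends the drug is listed as concomitant.
- A reader might infer that every patient has analgesics at risk. Criterion 5 also accepts paracetamol/acetaminophen, which Protocol 5.7.2 does not list among the drugs to be stopped.
- An ongoing drug with an unknown start still appears as concomitant and on-study. It is absent only from the Prior table.
- Low back pain medication history has its own eCRF (Protocol 6.3.1.3) and is named among baseline characteristics. However, the SAP specifies no table for it, so it does not make good the loss.
- The AE window is short, about 37 days from consent to first dose. A patient who already has another TEAE does not change the patient-level count.

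None of this supplies the missing check. A rule that can return a start later than a recorded end is wrong for those records, however few they are.

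**Conclusion.** The point holds in a limited form. For starts that are wholly missing, year-only in the dosing year, or in the dosing month, SAP 6.3 converts an AE with a recorded pre-dose end into a TEAE. For medications the result depends on the meaning of concomitant: under Protocol 5.7 a drug with such a start and a pre-dose end drops out of all the SAP 5.3 tables; under SAP 4.3 its handling is undefined. Either way the text needs correcting.

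The size cannot be computed from the documents. The rule ignores treatment arm, so a reader should not infer that it favours fasinumab or placebo. It adds non-treatment events to whichever arm the patient is in and can understate prior medication. No efficacy estimate or test is affected.

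**What to change.** Add to SAP 6.3:

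> Before imputing a start date, compare the recorded end date (or a partial end date that can only fall before first dose) with the first dose. If the end is before first dose, the imputed start may not be later than the end, and the record is classed as a pre-treatment AE or prior medication. An imputed start may never exceed the recorded end.

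Keep the existing first-dose rule for AEs and medications whose end date is missing or on or after first dose, and state that the start-date rule also applies to prior medications. Do not go further and class every medication with a wholly missing start as prior: that would put drugs first taken on study or in follow-up into the Prior table.

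The cost is a few sentences and a small change to the date derivation, applied identically in all arms. Since Protocol 9.6 carries the same rule, note the departure in SAP 1.1.5. Records whose partial end could fall on either side of first dose stay as they are, because their timing really is unknown.

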Patients will be instructed to stop using all prohibited medications at the pre-randomization visit. Patients will receive paracetamol/acetaminophen to be used as study-provided rescue medication. In the event of inadequate LBP relief, paracetamol/acetaminophen may be taken as needed, according to local standard of care, to a maximum total dose of 2600 mg (325 mg x 8) per day in North America and 2500 mg (500 mg x 5) per day in Europe, starting at the pre-randomization visit through week 16.

Patients must have a mean daily LBPI NRS score ≥ 4 during the pre-randomization period, in order to be eligible for study participation. Patients may not use paracetamol/acetaminophen for 48 hours prior to the start of a scheduled study visit or during a study visit, in order to minimize the confounding effects of rescue medication on efficacy measures.

Confirmation that there are no exclusionary findings on lumbar MRIs, any hip or knee MRI of joints with a K-L score ≥ 3 , or any other joint on which an MRI was performed during screening must be received before a patient can be randomized.

- **Treatment Period (day 1 through week 16):** The treatment period will begin at the randomization visit (baseline/day 1) and continue through the week 16 visit. Patients who meet study entry criteria will be randomized and will undergo baseline assessments at the day 1 visit. For patients randomized to SC administration, a loading dose equivalent to 2 times the maintenance dose will be administered on day 1.

Patients randomized to 6 mg or 9 mg fasinumab SC Q4W and placebo IV 9 mg Q8W will receive 2 SC injections of fasinumab on day 1 (SC loading dose), 1 SC injection at weeks 4, 8, and 12, and 1 IV infusion of matching placebo on day 1 and at week 8.

Patients randomized to 9 mg fasinumab IV Q8W and placebo SC Q4W will receive 1 IV infusion of fasinumab on day 1 and at week 8, 2 SC injections of matching placebo on day 1 (placebo for SC loading dose) and 1 SC injection of matching placebo at weeks 4, 8, and 12.

Patients randomized to placebo SC Q4W and placebo 9 mg IV Q8W will receive 2 SC injections of matching placebo to fasinumab on day 1 (SC loading dose), 1 SC injection of matching placebo at weeks 4, 8, and 12, and 1 IV infusion of matching placebo on day 1 and at week 8.

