6.2.4. Baseline/Randomization Visit (Day 1)

If a patient has met all screening eligibility criteria, study sites will complete the procedures as detailed in the schedule of events for the baseline visit. The patient reported outcomes assessments at this and subsequent visits should be completed prior to all other assessments. All laboratory samples at this and subsequent visits must be collected and all study procedures must be performed before study drug is administered. At dosing study visits, urine pregnancy testing will be done and read before the study drug is administered. In the event of a positive urine pregnancy test result, the patient should have a serum pregnancy test with a negative result in order to continue study participation. If the serum pregnancy test is positive, the patient should be withdrawn from study drug and should be asked to return to the clinic for all remaining study visits per the visit schedule (see [Section 6.2.7](#)).

The date of the first dose of study drug is designated as day 1. All subsequent visits should be scheduled based on this date.

6.2.5. Weeks 1 through 16

Complete visits and assessments are outlined in the schedule of events ([Table 1](#)). The patient reported outcomes should be completed prior to all other assessments. All study procedures should be completed before administration of study drug. The last dose of study drug is administered at week 12. Patients who discontinue study drug should return for the remaining study visits, if possible. If patients are not able to continue study participation, they should return for an early termination visit, at which the treatment-period early termination visit assessments will be performed per the schedule of events.

At dosing study visits, urine pregnancy testing will be done and read before the study drug is administered. Study drug will be withheld in the event of a positive urine pregnancy test result. In the event of a positive urine pregnancy test result, a serum pregnancy test must be performed. If the serum pregnancy test is negative, the patient may continue study participation. If the serum pregnancy test is positive, the patient must be permanently discontinued from study drug and should be asked to return to the clinic for all remaining study visits per the visit schedule ([Section 6.2.7](#)).

6.2.6. Weeks 20 through 36

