The U.S. Food and Drug Administration (FDA) placed the study on partial clinical hold before enrollment was completed and dosing was prematurely terminated before all randomized patients had completed treatment. The study was enrolling patients with chronic low back pain, some of whom had advanced osteoarthritis, to doses that exceeded those being pursued in the concurrent or planned osteoarthritis studies which limits dosing to 6 mg SC Q8W. Since an event of adjudicated arthropathy was observed in the CLBP study in a patient with advanced OA using a dose higher than that being evaluated in the ongoing OA study, the FDA requested that the study be placed on hold until the protocol could be amended to either remove patients with OA or reduce the doses. A decision was made not to amend the protocol to enable dosing to be resumed. At the time of the clinical hold, 563 patients had been randomized into the study. Patients will be encouraged to remain in the study and be followed for all study visits until completion of the week 36 visit to continue to monitor safety and to allow complete data collection.

The planned analyses take this change into account.

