2.1. Study Design and Randomization

The study consists of a screening period of up to 30 days (day -37 to day -8), a 7-day pre-randomization period (day -7 to day -1), a 16-week randomized, double-blind, placebo-controlled treatment period (to day 113), and a 20-week follow-up period (Figure 1). Approximately 800 patients will be randomized in a 1:1:1:1 ratio to one of the following 4 treatment groups:

- Fasinumab 6 mg SC Q4W and placebo 9 mg IV Q8W
- Fasinumab 9 mg SC Q4W and placebo 9 mg IV Q8W
- Fasinumab 9 mg IV Q8W and placebo SC Q4W
- Placebo SC Q4W and placebo 9 mg IV Q8W

Randomization will be stratified by baseline LBPI NRS score (<7 , ≥ 7), duration of chronic back pain (<5 years, ≥ 5 years), and maximum Kellgren-Lawrence (K-L) score (≤ 2 , > 2) at any knee or hip joint at screening. For patients randomized to SC administration, a loading dose equivalent to 2 times the maintenance dose will be administered on day 1.

Figure 1 Study Flow Diagram

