5.6.2. Exposure to Investigational product

The treatment exposure to fasinumab and placebo SC doses during the study will be presented by treatment and calculated as:

- (Date of last study drug administration – date of first study drug administration) + 28

The treatment exposure to fasinumab and placebo IV doses during the study will be presented by treatment and calculated as:

- (Date of last study drug administration – date of first study drug administration) + 56

The duration of exposure during the study will be summarized for each treatment group using the number of patients (n), mean, standard deviation, median, Q1, Q3, minimum, and maximum.

The number (%) of patients with exposure periods will be presented by specific time periods. The time periods of interest is specified as: ≥ 1 day, ≥ 8 days, ≥ 15 days, ≥ 29 days, ≥ 57 days, ≥ 85 days, and ≥ 113 days.

The duration of observation period during the study is calculated as:

- (Date of the last study visit – date of the first study drug administration) +1.

The number (%) of patients with observation periods will be presented by specific time periods. The time periods of interest is specified as: ≥ 1 day, ≥ 8 days, ≥ 15 days, ≥ 29 days, ≥ 57 days, ≥ 85 days, and ≥ 113 days.

A summary of the number of doses by treatment group will be provided.

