5.8. Analysis of Safety Data

The analysis of safety and tolerability will be performed on the SAF, as defined in [Section 3.3](#). The safety analysis will be based on the reported AEs and other safety information (clinical

laboratory evaluations, vital signs, physical exam and 12-lead ECG). Thresholds for Potential Clinically Significant Values (PCSV) in laboratory variables, vital signs and ECG are defined in [Appendix 10.2](#).

The summary of safety results will be presented for each treatment group.

Period of observation: The observation period will be divided into three segments: pre-treatment, on-treatment, and follow-up period.

- The pre-treatment period is defined as the time from signing the ICF to before the first dose of study drug.
- The on-treatment period is defined as the day from first dose of study drug to 4 weeks after the last dose of SC study drug or 8 weeks after the last dose of IV study drug, whichever is later.
- The Post/Treatment follow-up period is defined as from the end of the on-treatment period+1 day to the end of study visit (week 36).

Unless otherwise noted, summaries of safety variables will use data from the on-treatment period. Listings of safety variables will include data from all periods and values occurring during the pre-treatment and follow-up period will be flagged in the listings.

Day 1 is the first day of investigational product, Day –1 is the day before, and there is no Day 0.

The time interval to detect any on-treatment event or abnormality is the on-treatment period. Data collected outside this interval will be excluded from the estimation of descriptive statistics and identification of abnormalities for laboratory evaluations, ECGs and vital signs. All post-baseline data during the interval will be using in the PCSV analysis including scheduled and unscheduled assessments.

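### The SAP's fallback for an unknown last-dose date can place the last dose at the week 16 visit, when no dose is scheduled; it should be capped at the last dosing visit

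*SAP*

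**What the plan says.** SAP 6.3, in the paragraph on first and last injection dates, takes the first date from the CRF dosing module. For the last date it has a fallback: if the "date of the last dose is totally missing or unknown", then "his/her last visit date in the treatment period will be substituted".

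Protocol 3.1 defines the period that this refers to: "The treatment period will begin at the randomization visit (baseline/day 1) and continue through the week 16 visit". SAP 2.1 gives the same end as a study day: "placebo-controlled treatment period (to day 113". No dose falls at that visit. Protocol 6.2.5 states: "The last dose of study drug is administered at week 12". Under Protocol 5.1, SC injections are due on day 1 and at weeks 4, 8 and 12, and infusions on day 1 and at week 8.

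Three other parts of the SAP use the last-dose date:

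- **Exposure (5.6.2).** Last minus first administration, plus 28 days for SC. For IV the formula is "Date of last study drug administration – date of first study drug administration) + 56".
- **On-treatment period (5.8).** It runs until "4 weeks after the last dose of SC study drug or 8 weeks after the last dose of IV study drug, whichever is later". Treatment-emergent AEs are defined from this window (5.8.1).
- **Primary analysis (5.7.1).** Data are used up to the earliest of consent withdrawal, week 16, and 5 weeks after the last dose.

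**The concern.** The fallback uses attendance at visits as a stand-in for dosing. In this trial the two come apart. Protocol 5.3.2 asks patients who stop study drug to keep attending. The clinical hold ended dosing before all patients had finished treatment, and SAP section 1 adds: "Patients will be encouraged to remain in the study and be followed for all study visits until completion of the week 36 visit". A patient can therefore be off drug for weeks and still have week 16 as the last treatment-period visit.

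If the rule fires for such a patient, three things go wrong together. Exposure is overstated. AEs that began off drug are classed as treatment-emergent rather than post-treatment. Pain scores that the 5-week cut-off was meant to exclude enter the primary model. Even a patient who took every dose gets a date on which none was scheduled.

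**Working it through.** **Inputs.** Nominal dosing days are 1, 29, 57 and 85 for SC and 1 and 57 for IV (Protocol 5.1 and Table 1). Week 16 is day 113, with a window of day 106 to 120. The formulas are those of SAP 5.6.2, 5.8 and 5.7.1:

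- SC exposure = last SC − first + 28
- IV exposure = last IV − first + 56
- On-treatment end = later of (last SC + 28) and (last IV + 56)
- Primary data cut-off = earlier of day 113 and (last dose + 35), absent consent withdrawal

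**The plan's own figure.** On schedule, the on-treatment period ends at the later of 85 + 28 = 113 and 57 + 56 = 113. That is day 113, the week 16 end stated in Protocol 9.5.3.1. Exposure is (85 − 1) + 28 = 112 days SC and (57 − 1) + 56 = 112 days IV. The plan's formulas agree with its schedule when the last-dose date is right.

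**Case A: on-schedule completer, week 12 SC date missing, week 8 infusion date known.** The rule sets the last SC dose at day 113.

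**Case B: patient stopped after the week 4 SC dose, that date missing, still attending week 16.** The true last SC dose is day 29 and the only infusion was on day 1. The rule again gives day 113.

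| Quantity | A, true date | A, under the rule | B, true date | B, under the rule |
|---|---|---|---|---|
| SC exposure (days) | 84 + 28 = 112 | 112 + 28 = 140 | 28 + 28 = 56 | 112 + 28 = 140 |
| On-treatment end (day) | 113 | later of 141 and 113 = 141 | later of 57 and 57 = 57 | later of 141 and 57 = 141 |
| Primary data cut-off (day) | earlier of 113 and 120 = 113 | earlier of 113 and 148 = 113 | earlier of 113 and 64 = 64 | earlier of 113 and 148 = 113 |

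In case A exposure is 28 days too long and the on-treatment period 28 days too long; the primary analysis is unchanged. In case B both are 84 days too long, and scores at weeks 12 and 16 (days 85 and 113), which the true cut-off of day 64 excludes, enter the primary model.

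Across the week 16 visit window the imputed SC exposure runs from 105 + 28 = 133 to 119 + 28 = 147 days.

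**IV date, only if the rule is applied by route.** For a completer whose week 8 infusion date is missing, IV exposure becomes (113 − 1) + 56 = 168 days instead of 112, and the on-treatment period ends on day 113 + 56 = 169 instead of day 113. The SAP does not say whether the rule is run separately for each route.

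**The case against.** The strongest reply is that the rule may never fire. Stopping drug does not make a dosing date unknown. Doses are given at the site as the last procedure of the visit, the CRF has a dosing module, accountability records must carry dates (Protocol 5.6.3), and the IVRS collects drug usage (Protocol 10.2). This stands. A reader might infer that everyone stopped by the clinical hold would be counted as dosed to week 16. The documents do not support that: anyone with a recorded last-dose date is untouched.

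Three other stronger readings also fail.

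- **A patient dosed only on day 1 would be treated as dosed throughout.** That patient's last dose is the first dose. If the first date is recorded, the last is known and the rule does not apply. If it is not recorded, the exposure formula has no starting point.
- **Primary data would be kept to day 148.** The mITT definition in SAP 3.1, read alone, gives 113 + 35 = 148. SAP 5.7.1 also cuts at week 16, so the effective limit is day 113.
- **A missing infusion date is set at week 16 as a matter of course.** SAP 6.3 speaks of the patient's last dose. On a patient-level reading, a known later SC date means that a missing infusion date never triggers the rule.

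The consequences are also bounded. AE percentages use patient counts, and no exposure-adjusted rate is planned. SAP 5.8.1 tabulates post-treatment and combined AEs too, so no event is lost. A late date is cautious for counting treatment-emergent events and fits the SAP's other defaults for missing severity and causality. That caution does not justify overstated exposure or a later efficacy cut-off.

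**Conclusion.** The point holds as a small drafting error. Whenever the rule fires for a patient who attended week 16, it returns a date with no scheduled dose, and neither document limits it. The overstatement is 28 days of SC exposure and on-treatment time for a completer, with no effect on the primary analysis. It is 84 days of each for a patient who stopped after week 4 and stayed, with the primary cut-off moving from day 64 to day 113.

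These figures assume nominal visit days, attendance at week 16, a dose known to have been given but without a usable date, and no consent withdrawal before the cut-off. The IV figures also assume that the rule is run by route. The documents give no count of missing dates; the number affected may be zero.

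**What to change.** Replace the sentence in SAP 6.3 before database lock with, for example:

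> If the last-dose date is missing and cannot be recovered from IVRS or accountability records, substitute, separately by route, the date of the last scheduled dosing visit attended (SC: day 1, weeks 4, 8, 12; IV: day 1, week 8) on or before any recorded study-drug discontinuation date. The substituted date may not be later than the week 12 visit (SC) or the week 8 visit (IV).

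This settles the by-route question and still supplies a date when dosing records are silent. In case A it returns day 85, hence 112 days and day 113. In case B, with a discontinuation recorded before the week 8 visit, it returns day 29, hence 56 days, day 57 and a cut-off of day 64. If no discontinuation date was recorded, a stopper who kept attending would still be placed at the cap: SC exposure (85 − 1) + 28 = 112 days, so the error is reduced but not removed.

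The cost is one sentence and a lookup in records that the protocol already requires. The small downside is that slightly fewer AEs of uncertain timing count as treatment-emergent; they still appear in the post-treatment and combined tables. No treatment or visit changes.
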